## 2.2 Known Potential Benefits

The prognosis of multiple myeloma patients who become refractory to lenalidomide and bortezomib is very poor, indicating the need for new therapeutic strategies for these patients. Daratumumab has already shown marked activity as a monotherapy in heavily pre-treated patients. Its Breakthrough Therapy Designation from the FDA for patients who have been exposed to lenalidomide and bortezomib, highlights the potential clinical benefit of daratumumab therapy for the treatment of patients with relapsed/refractory multiple myeloma. The presence of severe renal dysfunction is an additional adverse feature of myeloma and requires immediate management, with effective, rapidly acting therapy. In this context daratumumab offers the most active therapy that is available for patients who have already been exposed and are relapsed or refractory to proteasome inhibitors and IMIDs and who present with severe renal impairment. Daratumumab has additional advantages related to the lack of effect of the degree of renal dysfunction or dialysis to PKs and pharmacodynamics of the monoclonal antibody. Thus, daratumumab with dexamethasone is likely to provide significant clinical benefit to subjects with relapsed or refractory multiple myeloma and renal impairment.

### 3. Objectives and Purpose

The purpose of this study is to evaluate the effects of daratumumab with dexamethasone in subjects with relapsed or refractory multiple myeloma and renal impairment.

#### 3.1 Primary objective

The primary objective of this study is to evaluate progression free survival (PFS) in subjects with relapsed or refractory multiple myeloma and renal impairment treated with daratumumab and dexamethasone.

#### 3.2 Secondary objectives

The secondary objectives of the study are the following:

- To evaluate Overall Response Rates (ORR)
- To evaluate Renal Response Rates (RRR)
- To evaluate duration of response (DoR) in patients with RI.
- To evaluate time to next therapy (TNT).
- To evaluate Overall Survival (OS).
- To assess the safety and tolerability of Daratumumab with dexamethasone in patients with RRMM and RI.

### 4. Study Design and Study End points

#### 4.1 Description of the Study Design

This is a multicenter, Phase 2, single arm, open-label study evaluating daratumumab with dexamethasone (DaraD) in subjects with relapsed or refractory multiple myeloma who have received at least two prior lines of treatment, with both bortezomib- and lenalidomide-based regimens and have renal impairment.

Approximately 38 subjects located in approximately 5 centers in Greece and 2 centers in Italy will receive daratumumab with dexamethasone. Treatment cycles have a duration of 28 days:

**Daratumumab** will be given at a dose of 16 mg/kg administered as an intravenous (IV) infusion at weekly intervals (QW) for 8 weeks, then every 2 weeks (Q2W) for an additional 16 weeks, then every 4 weeks (Q4W) thereafter. Subjects will receive pre-infusion medications before infusions to mitigate potential infusion reactions.

**Dexamethasone** will be administered according to standard clinical practice and at a recommended total dose of 40 mg weekly (20 mg weekly for patients >75 years of age).

Subjects will receive treatment until disease progression or unacceptable toxicity.

Drug administration and follow-up visits will occur more frequently for early cycles (e.g., weekly or bi-weekly) (see *Table 7.2*). Disease evaluations will occur monthly and consist mainly of measurements of myeloma proteins and renal function indices. Other parameters may include bone

marrow examinations, skeletal surveys, assessment of extramedullary plasmacytomas, and measurements of serum calcium corrected for albumin, and  $\beta$ 2-microglobulin and albumin.

Assessment of myeloma response and disease progression will be conducted in accordance with the modified International Myeloma Working Group (IMWG) response criteria (see [Appendix 4](#)).

Assessment of renal response will be conducted in accordance with the International Myeloma Working Group (IMWG) response criteria (see Appendix 5).

Survival status and data of subsequent anti-myeloma treatment will be collected post-treatment.

The maximum duration of the study is of 37 months considering an accrual period of 24 months and a follow-up of the last patient of 13 months.

#### **4.1.1 Primary Endpoint**

- Progression-free survival

#### **4.1.2 Secondary Endpoints**

- Overall response rate
- Renal Response rate
- Duration of response
- Time to next therapy
- Overall survival
- Safety (adverse events)

### **5. Study enrollment and withdrawal**

All criteria MUST be met to be included in the study.

#### **5.1 Participant Inclusion Criteria**

1. Males and females at least 18 years of age.
2. Voluntary written informed consent before performance of any study-related procedure.
3. Subject must have documented multiple myeloma as defined by the criteria below:

Monoclonal plasma cells in the bone marrow  $\geq 10\%$  or presence of a biopsy proven plasmacytoma. AND any or more of the following myeloma defining events:

- Evidence of end organ damage that can be attributed to the underlying plasma cell proliferative disorder, specifically:
  - Hypercalcaemia: serum calcium  $>0.25$  mmol/L ( $>1$  mg/dL) higher than the upper limit of normal or  $>2.75$  mmol/L ( $>11$  mg/dL)
  - Renal insufficiency: creatinine clearance  $<40$  mL per min or serum creatinine  $>177$   $\mu$  mol/L ( $>2$  mg/dL)
  - Anaemia: haemoglobin value of  $>20$  g/L below the lower limit of normal, or a haemoglobin value  $<100$  g/L
  - Bone lesions: one or more osteolytic lesions on skeletal radiography, CT, or PET-CT
- Any one or more of the following biomarkers of malignancy:
  - Clonal bone marrow plasma cell percentage  $\geq 60\%$
  - Involved:uninvolved serum free light chain ratio  $\geq 100$
  - $>1$  focal lesions on MRI studies

4. Prior treatment with at least two lines of treatment that included both bortezomib- and lenalidomide-based regimens.
5. Documented evidence of progressive disease (PD) as defined by the modified IMWG criteria (see [Appendix 4](#)) on or after the last regimen if the patient responded to previous regimens.
6. Subjects must have measurable disease as defined by any of the following:
  - Serum monoclonal paraprotein (M-protein) level  $\geq 1.0$  g/dL (except for IgA subtype:  $\geq 0.5$  g/dL) or urine M-protein level  $\geq 200$  mg/24 hours; or
  - Light chain multiple myeloma: Serum immunoglobulin free light chain  $\geq 10$  mg/dL (100 mg/L) and abnormal serum immunoglobulin kappa lambda free-light-chain ratio.
7. Renal impairment defined as eGFR  $< 30$  ml/min/1.73 m^2 (calculated with the CKD-EPI formula, see section 7.1.1.9) or in need for dialysis. Patients who undergo intraperitoneal dialysis may also be included.
8. Eastern Cooperative Oncology Group (ECOG) performance status score of  $\leq 2$ .
9. Willingness and ability to participate in study procedures.
10. Reproductive Status
  - a) Women of childbearing potential (WOCBP) must have two negative serum or urine pregnancy tests, one 10-14 days prior to start of the study drug and one within 24 hours prior to the start of study drug. Females are not of reproductive potential if they have been in natural menopause for at least 24 consecutive months, or have had a hysterectomy and/or bilateral oophorectomy.
  - b) Women must not be breastfeeding.
  - c) WOCBP must agree to follow instructions for methods of contraception for 4 weeks before the start of treatment with study drugs, for the duration of treatment with study drugs, and for 3 months after cessation of study treatment.
  - d) Males who are sexually active must always use a latex or synthetic condom during any sexual contact with females of reproductive potential, even if they have undergone a successful vasectomy. They must also agree to follow instructions for methods of contraception for 4 weeks before the start of treatment with study drugs, for the duration of treatment with study drugs, and for a total of 3 months post-treatment completion.
  - e) Male patients must not donate sperm for up to 90 days post treatment completion.
  - f) Female patients must not donate eggs for up to 90 days post treatment completion.
  - g) Azoospermic males and WOCBP who are not heterosexually active are exempt from contraceptive requirements. However, WOCBP will still undergo pregnancy testing as described in this section.

Highly effective methods of contraception have a failure rate of  $< 1\%$  when used consistently and correctly. Subjects must agree to the use of two methods of contraception, with one method being highly effective (tubal ligation, intrauterine device [IUD], hormonal [birth control pills, injections, hormonal patches, vaginal rings or implants] or partner's vasectomy) and the other method being additionally effective (male latex or synthetic condom, diaphragm, or cervical cap).

## 5.2 Participant Exclusion Criteria

1. Previous therapy with daratumumab or other anti-CD38 therapy.
2. Anti-myeloma treatment within 2 weeks prior to Cycle 1, Day 1.
3. Cumulative dose of corticosteroids greater than or equal to the equivalent of 140mg prednisone for  $\geq 4$  days or a dose of corticosteroids greater than or equal to the equivalent of 40 mg/day of dexamethasone for  $\geq 4$  days within the 2-week period prior to Cycle 1, Day 1.

4. Previous allogenic stem cell transplant; or Autologous Stem Cell Transplantation (ASCT) within 12 weeks before Cycle 1, Day 1.
5. Clinical signs of meningeal involvement of multiple myeloma.
6. Subject has either of the following:
  - a. Chronic obstructive pulmonary disease (COPD) with a Forced Expiratory Volume in 1 second (FEV1) <50% of predicted normal. Note that FEV1 testing is required for subjects suspected of having COPD and subjects must be excluded if FEV1 <50% of predicted normal.
  - b. Known moderate or severe persistent asthma (see Appendix 7), within 2 years from C1D1, or currently has uncontrolled asthma of any classification. Note that subjects who currently have controlled intermittent asthma or controlled mild persistent asthma are allowed to participate in the study.
7. Clinically significant cardiac disease, including:
  - a) Myocardial infarction within 1 year, or unstable or uncontrolled condition (e.g., unstable angina, congestive heart failure, New York Heart Association Class III-IV).
  - b) Uncontrolled cardiac arrhythmia (CTCAE Grade 2 or higher) (atrial fibrillation with controlled ventricular rate is allowed) or clinically significant ECG abnormalities.
  - c) ECG showing a baseline QT interval as corrected by Fridericia's formula (QTcF) >470 msec.
8. Any of the following:
  - a. Known active hepatitis A
  - b. Patient is seropositive for hepatitis B (defined by a positive test for hepatitis B surface antigen [HBsAg]). Subjects with resolved infection (ie, subjects who are HBsAg negative but positive for antibodies to hepatitis B core antigen [anti-HBc] and/or antibodies to hepatitis B surface antigen [anti-HBs]) must be screened using real-time polymerase chain reaction (PCR) measurement of hepatitis B virus (HBV) DNA levels. Those who are PCR positive will be excluded. EXCEPTION: Subjects with serologic findings suggestive of HBV vaccination (anti-HBs positivity as the only serologic marker) AND a known history of prior HBV vaccination, do not need to be tested for HBV DNA by PCR.
  - c. Known to be seropositive for hepatitis C (except in the setting of a sustained virologic response [SVR], defined as aviremia at least 12 weeks after completion of antiviral therapy).
9. Known to be seropositive for human immunodeficiency virus (HIV).
10. Amyloidosis, or any prior or concurrent malignancy, except for the following:
  - a) Adequately treated basal cell or squamous cell skin cancer.
  - b) Any cancer (other than in-situ) from which the subject has been disease-free for 3 years prior to study entry.
11. Any of the following laboratory test results during Screening:
  - a) Absolute neutrophil count  $\leq 1.0 \times 10^9/L$ ;
  - b) Hemoglobin level  $\leq 7.5 \text{ g/dL}$  ( $\leq 4.65 \text{ mmol/L}$ );
  - c) Platelet count  $< 75 \times 10^9/L$  in patients in whom < 50% of bone marrow nucleated cells are plasma cells and  $< 50 \times 10^9/L$  in patients in whom more than 50% of bone marrow nucleated cells are plasma cells;
  - d) Alanine aminotransferase level  $\geq 2.5$  times the upper limit of normal (ULN);
12. Pregnant or nursing women.

## 5.3 Participant Withdrawal or termination

### 5.3.1 Reasons for Withdrawal or Termination

Every patient has the right to discontinue study participation at any time, for any reason, and every patient may be discontinued from the study for any reason beneficial to his/her wellbeing.

Subjects MUST discontinue investigational product for any of the following reasons:

- Withdrawal of informed consent.
- Any adverse event (AE), laboratory abnormality or intercurrent illness that, in the opinion of the investigator, indicates that continued participation in the study is not in the best interest of the subject.
- Progressive Disease.
- Grade 4 Infusion Related Reactions (IRR) to daratumumab or in case of 3 recurrences of a  $\geq$  Grade 3 IRR during one infusion (*see Appendix 2*).
- When the study ends/is terminated.

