## 6.1.5 Dose Adjustments/Modifications/Delays

### ➤ Daratumumab

No dose adjustment or modification is permitted for daratumumab. Infusion reactions may lead to the interruption of IV daratumumab administration. Pre-infusion medications should be administered to reduce the risk of infusion-related reactions (IRRs) prior to treatment.

For IRRs of any grade/severity, immediately interrupt daratumumab infusion and manage symptoms. The management of IRRs may further require reduction in the rate of infusion, or treatment discontinuation of daratumumab as outlined below.

- Grade 1-2 (mild to moderate): Once the patient's condition is stable, the infusion should be resumed at no more than half the rate at which the IRR occurred. If the patient does not experience any further IRR symptoms, infusion rate escalation may be resumed at increments and intervals as clinically appropriate up to the maximum rate of 200 mL/hour.

- Grade 3 (severe): Once reaction symptoms resolve, restarting of the infusion may be considered at no more than half the rate at which the reaction occurred. If the patient does not experience additional symptoms, infusion rate escalation may be resumed at increments and intervals as appropriate. The procedure above should be repeated in the event of recurrence of Grade 3 symptoms. Permanently discontinue daratumumab if the patient experiences a  $\geq$  Grade 3 infusion-related symptom at the subsequent infusion.
- Grade 4 (life threatening): Permanently discontinue daratumumab treatment.

See [Appendix 2](#) for further guidelines concerning the administration of daratumumab.

See the Summary of Product Characteristics for more details about daratumumab

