### Management of infusion-related reactions

Pre-infusion medications should be administered to reduce the risk of infusion-related reactions (IRRs) prior to treatment with DARZALEX.

For IRRs of any grade/severity, immediately interrupt the DARZALEX infusion and manage symptoms.

Management of IRRs may further require reduction in the rate of infusion, or treatment discontinuation of DARZALEX as outlined below.

- Grade 1-2 (mild to moderate): Once the patient's condition is stable, the infusion should be resumed at no more than half the rate at which the IRR occurred. If the patient does not experience any further IRR symptoms, infusion rate escalation may be resumed at increments and intervals as clinically appropriate up to a maximum rate of 200 mL/hour (Table above).
- Grade 3 (severe): If the intensity of the IRR decreases to Grade 2 or lower, restarting of the infusion may be considered at no more than half the rate at which the reaction occurred. If the patient does not experience additional symptoms, infusion rate escalation may be resumed at increments and intervals as appropriate (Table above). The procedure above should be repeated in the event of recurrence of Grade 3 symptoms. Permanently discontinue DARZALEX if the patient experiences a  $\geq$  Grade 3 infusion-related symptom at the subsequent infusion.
- Grade 4 (life threatening): Permanently discontinue DARZALEX treatment.

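### The mandatory stop in Protocol 5.3.1 after three recurrences of a Grade 3 or higher infusion reaction cites Appendix 2, but neither Appendix 2 nor 6.1.5 contains it, and the three places do not give the same set of conditions

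*Protocol*

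**What the plan says.** Protocol 5.3.1 introduces its list with "Subjects MUST discontinue investigational product for any of the following reasons". The entry on infusion reactions begins "Grade 4 Infusion Related Reactions (IRR) to daratumumab or in case of 3 recurrences of a", sets the threshold at Grade 3 or above, fixes the time frame as "Grade 3 IRR during one infusion", and sends the reader to Appendix 2.

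Protocol 6.1.5, under Daratumumab, allows a restart at a reduced rate to be considered after a Grade 3 reaction. It then adds: "The procedure above should be repeated in the event of recurrence of Grade 3 symptoms". Its permanent stop comes later: "Permanently discontinue daratumumab if the patient experiences a" Grade 3 or higher symptom at the following infusion.

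Appendix 2, on management of infusion-related reactions, has the same repeat instruction. Its stop rule starts "Permanently discontinue DARZALEX if the patient experiences a", and the trigger, again with Grade 3 as the minimum, is a "Grade 3 infusion-related symptom at the subsequent infusion". For the most severe reactions it says "Grade 4 (life threatening): Permanently discontinue DARZALEX treatment".

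Protocol 6.1.6 refers to Section 5.3 for the discontinuation criteria other than progression and unacceptable toxicity, so the 5.3.1 list serves as a reference point elsewhere in the protocol.

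**The concern.** A permanent stop for severe infusion reactions is a safety rule, and staff giving the infusion are most likely to have 6.1.5 or Appendix 2 in front of them. Neither shows the stop that 5.3.1 makes mandatory, and following the cross-reference from 5.3.1 does not lead to it. A site could follow Appendix 2 faithfully and still breach 5.3.1.

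What is at stake is, first, the safety of a patient with repeated severe reactions in one infusion. Second is bookkeeping: whether continued treatment counts as a protocol deviation depends on which section the monitor reads. Deviation status feeds the Per Protocol Set (Protocol 10.3, SAP 6.5.2), and stopping decisions feed the exposure and disposition summaries (Protocol 10.4.5 and 10.4.6; SAP 6.6.1 and 6.6.1.6).

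**Working it through.** The stopping rules involve no calculated figure, so the check sets the three current texts side by side.

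| Situation | 5.3.1 | 6.1.5 | Appendix 2 |
|---|---|---|---|
| Grade 4 reaction | Stop | Stop permanently | Stop permanently |
| Three recurrences, Grade 3 or higher, in one infusion | Stop | Not mentioned; Grade 3 restart procedure repeated, no maximum given | Not mentioned; Grade 3 restart procedure repeated, no maximum given |
| Grade 3 or higher symptom at the subsequent infusion | Not in the list | Stop permanently | Stop permanently |
| When a Grade 3 restart may be considered | Not covered | Symptoms have resolved | Intensity has fallen to Grade 2 or below |

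1. **Grade 4.** All three agree.

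2. **Third Grade 3 recurrence within one infusion.** 5.3.1 requires a stop. Under 6.1.5 and Appendix 2 a reader finds only the repeat instruction. The rest of Appendix 2 (infusion rates, medication before and after the infusion, prophylaxis) contains no recurrence count either, so the cross-reference is false. The Amendment 1 log gives Appendix 2 as the reason for adding the entry to 5.3.1. That indicates the pointer was meant as the source of the rule; the finding itself rests on the current text.

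3. **Grade 3 at one infusion, Grade 3 or higher at the next.** 6.1.5 and Appendix 2 require a permanent stop. The infusion-reaction entry in 5.3.1 is not met. Nothing in 5.3.1 says to continue, so this is an omission from the list.

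4. **Grade 3 reaction that has eased to Grade 2 or lower but has not resolved.** Appendix 2 lets a restart be considered; 6.1.5 does not yet.

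**Size.** The documents give no rate for the situations in steps 2 to 4. The nearest figure bears on step 3 only. Protocol 6.1.4 says that 4% of patients had a reaction at more than one infusion, with no restriction by grade. If that rate carried over to the 38 planned patients (an assumption, since the population differs), 0.04 x 38 = 1.5 patients would react at more than one infusion. Those with Grade 3 or higher reactions at consecutive infusions are a subset of these. For step 2 there is no usable figure.

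**The case against.** The best defence is that the rules can be read together. 6.1.5 and Appendix 2 do not order a restart after a Grade 3 reaction; they allow one to be considered. A permissive procedure without a count fits with a mandatory cap stated elsewhere: restarts may be considered until the 5.3.1 limit is reached. A reader might infer that the sections issue opposite commands, or that 6.1.5 and Appendix 2 authorise unlimited restarts. The text does not support either reading: the absence of a maximum is silence, not permission. What survives is that the protocol nowhere says the rules are cumulative, no single section holds the full set, and the citation is wrong.

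A reader might also treat the subsequent-infusion stop as a contradiction. It is not. 5.3.1 does not claim to be exhaustive, and other stop rules also sit outside it, such as those in 6.1.5 for toxicity holds of more than 28 days and for three or more consecutive missed doses. A site that follows the whole protocol stops the drug. The general adverse-event entry in 5.3.1 could also cover such a patient, although it depends on the investigator's judgement.

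Finally, Protocol 1.2 quotes a 5% Grade 3 rate for daratumumab with lenalidomide and dexamethasone. From this one might compute 0.05 x 38 = 1.9 expected patients and 1 - 0.95^38 = 0.86 as the chance of at least one, and take these as the size of the problem. They are not. They count any Grade 3 reaction, and a single one triggers neither disputed stop. The rate also comes from a different regimen, in patients with a median of one prior line. A Grade 3 reaction is the entry point for the restart mismatch, but that bites only if a restart is considered before symptoms have fully resolved, for which no rate is given. Protocol 1.2 also reports that no patient in the two monotherapy studies discontinued because of an infusion reaction, which points to rarity.

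**Conclusion.** The protocol is internally inconsistent on a mandatory stopping rule. The within-infusion stop appears only in 5.3.1, under a cross-reference that does not hold, and sites using 6.1.5 or Appendix 2 alone would miss it. The 5.3.1 list is incomplete on the subsequent-infusion stop. The Grade 3 restart condition differs between 6.1.5 and Appendix 2.

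The stop triggers are likely rare, and their frequency cannot be estimated from the documents. At most an occasional patient's stopping date, discontinuation reason or deviation status would change. Whether such a deviation would remove a patient from the Per Protocol Set cannot be settled, because SAP 6.5.2 repeats that the excluding deviations will be defined in the SAP and does not list them.

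The sample size does not depend on any of this. Nor does the primary PFS analysis: it uses the Full Analysis Set, stopping the drug is neither an event nor in itself a reason for censoring (Protocol 10.4.2), and patients who stop before progression continue to be assessed every 4 weeks (Protocol 7.2.3). The case for correction rests on patient safety and clear deviation handling.

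**What to change.** The sponsor must reconcile Protocol 5.3.1, 6.1.5 and Appendix 2 so that all three state the same complete set of permanent-discontinuation conditions for infusion reactions and the same condition for considering a restart after a Grade 3 reaction, and so that the pointer from 5.3.1 to Appendix 2 is true. The restart condition should be settled in the same edit; otherwise that mismatch would remain. Which conditions apply is a clinical decision for the sponsor, and no view on it is taken here.

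The cost is wording in three places at the next amendment and a notice to sites. No change to the sample size or the analysis methods is needed.
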